## **6 SELECTION AND WITHDRAWAL OF SUBJECTS**

### **6.1 Inclusion criteria**

To be eligible to participate in this study, all of the following criteria must be met:

1. An Institutional Review Board (IRB)/Independent Ethics Committee (IEC) approved written Informed Consent form is signed and dated by the subject.
2. The subject is considered reliable and capable of adhering to the protocol visit schedule, or medication intake according to the judgment of the investigator.
3. Subject is  $\geq 18$  years of age at Visit 1 (Screening).

4. Subject has a documented definite or probable diagnosis of CIDP according to the EFNS/PNS criteria 2010.
5. Subject has an Ig-dependency confirmed by clinical examination during therapy or upon interruption or reduction of therapy within 18 months prior to Screening and documented in medical history (ie, that a decrease or withdrawal of immunoglobulin was attempted that resulted in a clinically relevant decrease in function).
6. Subject is on a stable dosage (not more than  $\pm 20\%$  deviation) for SC Ig or IV Ig and a fixed interval for at least 4 months of either treatment, eg, once weekly  $\pm 2$  days for SC Ig or every 2 to 6 weeks  $\pm 5$  days IV Ig, respectively, for stability in functioning between dosing.
7. Female subjects of childbearing potential must have a negative serum pregnancy test at the Screening Visit, which is confirmed to be negative by urine testing prior to the first dose of IMP at Week 1 (Visit 2) and prior to further dosing at each study visit thereafter.

Female subjects of childbearing potential must agree to use a highly effective method of birth control, during the study and for a period of 3 months after their final dose of IMP. Highly effective forms of birth control are methods which achieve a failure rate of less than 1% per year when used consistently and correctly. According to the International Council for Harmonisation (ICH) M3 R2, highly effective methods of birth control include:

- Combined (estrogen- and progesterone-containing) hormonal contraception (oral, implant, injectable) associated with inhibition of ovulation (which must be stable for at least 1 full month prior to Screening [Visit 1], and should remain stable during the study).
- Progesterone-only hormonal contraceptives (oral, implant, injectable) associated with inhibition of ovulation (which must be stable for at least 1 full month prior to Screening [Visit 1], and should remain stable during the study).

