### **8.3 12-Week Observation Period Visits 17 to 21 (Day 85 to Day 162)**

Following the final dose of rozanolixizumab or placebo at Day 78 (Visit 16), 5 subsequent visits will be scheduled over 12 weeks (Visit 17 through Visit 21) to collect safety and efficacy data for study related outcome measures and procedures. Visit 18 and Visit 20 are home nursing visits to be conducted by a healthcare professional visiting the subject at his/her home; these visits can be conducted at the site as deemed necessary by site personnel and/or subject.

Visit 17 will be the last study visit for the subjects entering immediately in the OLE study upon completing all visits in the Treatment Period.

All subjects not entering the OLE immediately should perform all visits of the Observation Period, including the Final Visit (scheduled 12 weeks after the final dose of IMP).

If at any time during the Observation Period, the subject relapses according to the predefined criteria for relapse as specified in Section 4.1.2 using the subject's score on iRODS, INCAT, or maximum grip strength (assessed by site personnel), and supported by the medical judgement of the investigator, then rescue medication must be considered. The subject will return to the SOC (ie, Ig treatment) as rescue medication at the time of relapse and will be stabilized over a period ranging from 2 weeks to maximum 12 weeks starting from time of relapse. During the stabilization, visits should be performed every 1 to 3 weeks at the discretion of the investigator until the subject is stabilized. The stabilization may extend the Observation Period duration up to a maximum of 24 weeks after last IMP dose. At the end of the stabilization, the subjects who complete the Treatment Period without a CIDP relapse will be offered the possibility to enter in the OLE immediately and be treated with rozanolixizumab. Their last visit in the study will be the FV, scheduled at the end of stabilization and enter the OLE on the same day. Assessments performed at the FV will not be repeated in the OLE.

If the subject does not wish to/cannot enter the OLE, the subject will continue treatment with SOC. The time required for follow-up since last IMP dose is 12 weeks. The stabilization visit schedule still applies (every 1 to 3 weeks) if the subject has not reached 12 weeks post last IMP dose at the end of stabilization.

Table 8–1 summarizes the options for the subject to proceed in the Observation Period.

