#### **12.1.3      Follow up of adverse events**

An AE should be followed until it has resolved, has a stable sequelae, the investigator determines that it is no longer clinically significant, or the subject is lost to follow up. This follow-up requirement applies to AEs, SAEs, and AEs of special interest; further details regarding follow up of PDILI events is provided in Section 12.2.1.4.

If an AE is ongoing at the end of the study for a subject, follow up should be provided until resolution/stable level of sequelae is achieved, or until the investigator no longer deems that it is clinically significant, or until the subject is lost to follow up. If no follow up is provided, the investigator must provide a justification. The follow up will usually be continued for 12 weeks after the subject has discontinued his/her IMP.

Information on SAEs obtained after clinical database lock will be captured through the Patient Safety (PS) database without limitation of time.

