### **18.5 Protocol amendment 2**

#### **Rationale for the amendment**

The purpose of this substantial protocol amendment is to provide clarification on the dose of investigational product administered (including an allowance of  $\pm 10\%$  compared to the [REDACTED] target dose arm), as well as a flexible infusion rate. Sensitivity analyses were introduced to account for deviation outside the  $\pm 10\%$  target dosage and the descriptive analyses will inform about actual doses administered to the subjects. Updates to the status of the other

rozanolixizumab studies have been included. The visit windows and the scheduling of the randomization visit in view of the Ig treatment at study start have been clarified. The predominance of objective criteria over the investigator's judgement has been confirmed for the assessment of CIDP relapse. The timeframe of expected use of contraception post-study completion has been extended to 90 days in view of the probable half-life of rozanolixizumab. Exclusion criterion #3 has been extended to prediabetic condition. The expectation with regards to the use of cannabinoids and medicinal marijuana has been clarified in the concomitant medication section. The protocol amendment confirms the expectation of a single rater for the INCAT assessment to ensure consistency of the rating during the course of the study.

In addition, some administrative changes have been made.

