## 10.2 Adverse events

Adverse events will be recorded from the time of informed consent until study completion. All AEs will be coded (Section 3.8) and categorized by relationship to rozanolixizumab.

In addition, AEs will be classified according to the Common Terminology Criteria for Adverse Events (CTCAE) Version 5.0 for severity. For any AEs where it is not possible to provide a CTCAE grading, the events will be assessed using a standard intensity classification (mild, moderate and severe).

A TEAE is defined as any event that was not present prior the first administration of IMP or any unresolved event already present before the first administration of IMP that worsens in intensity following exposure to treatment until 8 weeks following the last administration of IMP. Adverse events starting before the first administration of IMP or later than 8 weeks after the administration of the last IMP will not be considered TEAEs. Such events will be listed only.

Where dates are missing or partially missing, AEs will be assumed to be treatment-emergent unless evidence exists that does not allow the AE to be treatment-emergent. Handling of missing dates/times for classification of AEs as TEAEs is described in Section 4.2.7.

The following rules will be used to assign a TEAE to the study periods:

1. **Treatment Period:** a TEAE will be assigned to the Treatment Period for the tabulations if the start date/time of the event is at the time of or after the first administration of IMP on Day 1, up to Visit 17/PEOT (non-inclusively).
2. **Observation Period:** a TEAE will be assigned to the Observation Period for the tabulations if the start date/time of the event is at or after Visit 17/PEOT till 8 weeks after administration of the last IMP.
  - The Observation Period's TEAEs will be stratified by TEAEs of participants who received/did not receive standard of care treatment (i.e. Ig treatment) between start of the Observation Period and occurrence of the TEAE.

The number and percentage of participants who experience TEAEs will be summarized by Treatment Period, Observation Period (standard of care treatment status identified by WHODD J06BA01 and J06BA02) and Overall with respective treatment group. The following summaries will be presented:

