- Incidence of TEAEs (overview including number and percentage of participants with any TEAEs, serious TEAEs, discontinuations due to TEAEs, related TEAEs, TEAEs with CTCAE Grade 3 and above [or rated as 'severe' for events with no CTCAE classification], and deaths; event counts will also be included)
- Incidence of TEAEs by SOC, HLT and PT
- Incidence of TEAEs during the Dosing Period by SOC, HLT and PT
- Incidence of serious TEAEs by SOC, HLT and PT
- Incidence of non-serious TEAEs by SOC, HLT and PT
- Incidence of AEs of special interest by SOC, HLT and PT
- Incidence of AEs of interest by SOC, HLT and PT

- Incidence of TEAEs by relationship, SOC, HLT and PT
- Incidence of TEAEs by maximum relationship, SOC, HLT and PT
- Incidence of serious TEAEs by relationship, SOC, HLT and PT
- Incidence of non-serious TEAEs by relationship, SOC, HLT and PT
- Incidence of fatal TEAEs by relationship, SOC, HLT and PT
- Incidence of TEAEs by maximum intensity (mild, moderate and severe), SOC, HLT and PT
- Incidence of non-serious TEAEs above threshold of 5% of participants by SOC and PT
- Incidence of non-serious TEAEs above threshold of 5% of participants by relationship, SOC and PT
- Discontinuation due to AEs

Summary tables will contain counts of participants, percentages of participants in parentheses and the number of events. A participant who has multiple events in the same SOC, HLT and PT will be counted only once in the participant counts but all events will be included.

Adverse event summaries will be ordered by alphabetical SOC, alphabetical HLT within SOC and decreasing frequency in the active treatment group.

In summaries including intensity, the CTCAE categories will be summarized according to the following categories:

- Grade 1: Mild
- Grade 2: Moderate
- Grade 3: Severe
- Grade 4: Severe
- Grade 5: Severe
- not gradable

In the case both category types are captured and the mapping to a standard intensity classification per above rule results in a class different from the standard intensity classification given in the eCRF, the worst case will be used.

These will be tabulated together with the AEs that were not classified according to CTCAE criteria i.e., all Grade 1 AEs as per CTCAE criteria will be included in the 'mild' category together with those AEs classified as mild as per the 'standard' intensity classification.

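### The SAP ends treatment emergence 8 weeks after the last dose, so AEs starting in the last 4 of the 12 planned post-dose weeks are listed but left out of the TEAE tables

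*SAP*

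**What the plan says.** SAP 10.2 sets collection and counting differently. On collection: "Adverse events will be recorded from the time of informed consent until study completion". On counting, an event assigned to the Observation Period must start "at or after Visit 17/PEOT till 8 weeks after administration of the last IMP", and events starting "later than 8 weeks after the administration of the last IMP will not be considered TEAEs. Such events will be listed only".

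Most of the planned AE tables are TEAE tables: serious and non-serious events, relationship, maximum intensity, and "Incidence of fatal TEAEs by relationship, SOC, HLT and PT". SAP 10.2 also defines AEs of focus, which include opportunistic infections and drug-related hepatic disorders, as TEAEs.

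Planned follow-up is longer. Protocol 8.3 says that after the final dose on Day 78, "5 subsequent visits will be scheduled over 12 weeks (Visit 17 through Visit 21) to collect safety and efficacy data". Protocol 5.1.1 and SAP 3.2.2 give an Observation Period of 12 to 24 weeks, shortened to 1 week for a participant who goes straight into the OLE. Protocol 12.1.2.3 collects SAEs until 30 days after a participant's study end.

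**The concern.** Safety and tolerability is the first secondary objective (Protocol 3.2), and the Observation Period visits exist partly to serve it. If counting stops before follow-up does, the serious and fatal TEAE tables describe less than the trial observed. A serious infection starting in week 10 after the last dose would be in the listing but in neither the serious TEAE table nor the opportunistic-infection focus table.

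The participants still under observation then are those who did not enter the OLE at Visit 17: people who relapsed, stopped treatment early, returned to standard-of-care immunoglobulin (Ig), or chose to test whether they still need treatment. The arms are small. With 34 participants randomized 1:1 there are 17 per arm, so one participant is 1/17 = 5.9% of an arm, and one uncounted event visibly moves a by-arm rate.

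**Working it through.** **Inputs.** Last dose Day 78 (Protocol 8.3). Visits 17 to 21 on Days 85, 99, 120, 141 and 162 (Protocol Table 5–1). TEAE limit 8 weeks = 56 days (SAP 10.2). Treatment Period 11 weeks. Post-dose follow-up W = 1, 12 or up to 24 weeks (SAP 3.2.2).

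**Plan's own figure.** (162 − 78)/7 = 12.0 weeks, which reproduces the stated 12-week Observation Period.

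**Where the window closes.** 78 + 56 = Day 134. Visits 17, 18 and 19 fall 1, 3 and 6 weeks after the last dose. Visits 20 and 21 fall at 9 and 12 weeks.

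**Share of post-dose follow-up outside the window**, max(0, W − 8)/W:

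- W = 12: 4/12 = 33.3% (28 of 84 days)
- W = 24: 16/24 = 66.7% (112 of 168 days)
- W = 1 (direct OLE entry): 0%

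**Share of all follow-up from first dose**, max(0, W − 8)/(11 + W):

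- W = 12: 4/23 = 17.4%
- W = 24: 16/35 = 45.7%

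**Onset, not visit date.** The exclusion is by start date. Visit 20 collects events arising since Visit 19, and 134 − 120 = 14 of those 21 days are still inside the window. Only the Visit 20 to Visit 21 interval lies wholly outside.

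**What happens to an AE with later onset:**

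- *Not counted:* the serious, fatal, relationship, intensity and AE-of-focus tables, which are restricted to TEAEs.
- *Unclear:* the deaths item in the overview, and the tables of AEs of special interest, AEs of interest and discontinuation due to AEs. Their labels do not say TEAE. However, the sentence introducing the list is about TEAEs, the deaths item sits inside the TEAE overview, and later-onset events are said to be listed only. Two programmers could treat a later-onset fatal event differently.
- *Still visible:* the listing of all AEs by treatment group, with SAE flags and days since the most recent dose (SAP 10.2). The disposition table counts discontinuations due to AEs without a window (SAP 5.1).
- *Separate route for liver tests:* SAP 10.3.1 tabulates participants meeting potential drug-induced liver injury criteria at any visit. Chemistry is drawn at Visit 21 and every 4 to 6 weeks in stabilization (Protocol 8.3.2 and 8.3.3).

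**The case against.** The strongest reply is that the SAP has filled a gap and hidden nothing. The protocol defines no TEAE window and leaves statistical detail to the SAP, so a reader who infers an undeclared departure that SAP 3.9 should have recorded goes further than the documents allow. That reply stands.

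The passages that seem to call for a longer window are also weaker than they look. Protocol 12.1.3 says "The follow up will usually be continued for 12 weeks after the subject has discontinued his/her IMP", but this concerns following an existing AE to its outcome, not the onset period for treatment emergence. The rationale for Amendment 2 says the contraception period "has been extended to 90 days in view of the probable half-life of rozanolixizumab", but that addresses pregnancy risk. The protocol uses different post-dose periods for different purposes: live vaccination is barred for 7 weeks after the final dose. Neither passage shows that 8 weeks is wrong.

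A reader might also infer that late events, deaths included, reach no summary table at all. The documents do not support that, given the laboratory liver table, the disposition table and the open scope of the deaths item. A death in week 10 from an event that began in week 7 also remains a fatal TEAE as long as the event keeps its week-7 start date. Protocol 12.1.2.2 enters a worsening as a repeated AE with a new start date, so even this depends on how the event is recorded.

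Finally, simply lengthening the TEAE window has a real cost. Follow-up after Visit 17 is a post-randomization subset. Direct OLE entry requires no relapse, so observation time may differ by arm, and many of those remaining may be back on Ig. Splitting by Ig status does not correct unequal follow-up. This is a good reason not to extend the window. It is no reason to leave later events without a separate count.

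**Conclusion.** The point holds in a limited form. For participants followed the planned 12 weeks, AEs and SAEs starting in the last third of post-dose follow-up (4 of 12 weeks) are excluded from the TEAE-based tables. The figure is 67% only in the longest stabilization case and zero for direct OLE entrants. Counted from first dose, the shares are 17.4% and 45.7%.

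The 8-week limit contradicts no protocol definition. It is shorter than the safety follow-up the trial pays for, and the SAP gives no reason for it. Nothing else in the SAP supplies a by-arm table of later-onset SAEs. The scope of the deaths, special-interest, of-interest and discontinuation counts needs to be stated.

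The day counts assume that all doses are taken on the nominal schedule. The documents do not say how many participants will be followed beyond 8 weeks, so the number of events affected cannot be estimated. Because late events remain listed by arm with SAE flags, this is a worthwhile, cheap improvement in reporting and not a loss of data.

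**What to change.** In SAP 10.2:

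1. Keep the 8-week TEAE definition and give the reason for it.
2. Add by-arm tables of AEs, SAEs and deaths with onset more than 8 weeks after the last IMP, up to the Final Visit. Split them by standard-of-care Ig status, as already planned for Observation Period TEAEs.
3. Use the number of participants still followed beyond 8 weeks in each arm as the denominator, and show it.
4. State that the deaths, special-interest and of-interest counts cover all events after first dose, and state the scope of the discontinuation table.

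The cost is SAP wording and a few tables from data already collected. The new tables describe a selected subset with unequal follow-up, so they should be labelled descriptive and not read as a randomized comparison.

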## 6.4 Withdrawal criteria

Subjects are free to withdraw from the study at any time, without prejudice to their continued care.

Subjects **MUST be withdrawn from the study** if any of the following events occur:

1. Subject withdraws his/her consent.
2. Subject becomes pregnant during the study, as confirmed by a positive pregnancy test.

Subjects **must discontinue IMP** if any of the following events occur:

1. Subject develops an illness that would interfere with his/her continued participation.
- Subject has a serious infective episode requiring hospitalization or iv antibiotic therapy (including but not limited to bacteremia or sepsis, bacterial meningitis, osteomyelitis or septic arthritis, bacterial pneumonia, or visceral abscess).
- Subject has an AE of severe infusion reaction requiring corticosteroid and/or epinephrine therapy (see Section 12.1.9).
- Subject has an AE of severe anaphylactic reaction requiring corticosteroid and/or epinephrine therapy.
- Subject has a TB test that is confirmed positive or any further evidence suggestive of potential TB infection (eg, exposure) and further examinations result in a diagnosis of active TB or LTBI (refer to Section 12.3.7 for further details and instructions).
- If a nontuberculosis mycobacterium infection (NTMBI) is identified during a study, the same withdrawal procedures as those used for an active TB infection identified during the study should be followed.
2. Subject has active suicidal ideation as indicated by a positive response (Yes) to either Question 4 or Question 5 of the “Since Last Visit” version of the C-SSRS. The subject should be referred immediately to a Mental Healthcare Professional.
3. The sponsor or a regulatory agency requests withdrawal of the subject.
4. Subject needs or takes PLEX, dexamethasone or rituximab.
5. Subject is treated with rescue medication and/or relapses during the Treatment Period (refer to Section 7.7.3).

Subjects **may be discontinued from IMP** at the discretion of the investigator, Medical Monitor, and Study Physician if any of the following events occur:

1. Subject takes prohibited concomitant medications during the Treatment Period as defined in this protocol (refer to Section 7.7.2).

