### 2.3 Study design and conduct

This is a Phase 2A, multicenter, randomized, subject-blind, investigator-blind, placebo-controlled, parallel-group study evaluating the efficacy, safety, and tolerability of rozanolixizumab for treatment of subjects with CIDP. Eligible subjects will be adults who have a confirmed diagnosis of definite or probable CIDP according to the European Federation of Neurological Societies (EFNS)/ Peripheral Nerve Society (PNS) criteria for CIDP, have been shown to be dependent on treatment with immunoglobulin and who have remained on a stable dosing regimen of immunoglobulin therapy for at least 4 months prior to Screening.

- Treatment Arm 1: rozanolixizumab [REDACTED]  
[REDACTED]
- Treatment Arm 2: placebo sc [REDACTED]  
[REDACTED]

Subjects will be randomized in a ratio of 1:1 to the 2 treatment arms. The randomization will take place on the day of first treatment with investigational medicinal product (IMP). The randomization will be stratified according to previous route of administration for Ig treatment (ie, subcutaneous immunoglobulin (SCIg) and intravenous immunoglobulin (IVIg)).

The dose level of [REDACTED] may be reduced to [REDACTED] (or equivalent placebo) for an individual subject based on their tolerability.

The study consists of:

- Screening Period of between 2 and 5 weeks duration
- The 11-week Treatment Period
- The 12-week Observation Period (from 1 week up to maximum 24 weeks):
  - All subjects completing the Treatment Period (ie, all visits up to Visit 17 performed without a CIDP relapse) will be offered the possibility to enter in the Open-Label Extension (OLE) study, CIDP04, and be treated with rozanolixizumab. If they enter in the OLE, Visit 17 will be the last study visit. The Observation Period will be limited to 1 week for these subjects.

In all other instances the subjects will perform Visits 18 to 21 for efficacy and for safety assessments. Subjects will either return to the clinic/hospital, or, if possible and agreed by both investigator and subject, have home visits conducted by certified healthcare professionals for Visits 18 and 20.

---

- For subjects who complete the Treatment Period without relapse but choose not to enter the OLE directly and wish to first test whether they still need treatment, they will continue the Observation Period without standard of care treatment.

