## 10 SAFETY ANALYSES

All safety analyses will be presented using the SS Listings will be presented by treatment group and participant; tabulations will be presented by visit/timepoint (if applicable) and treatment group.

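### TEAE percentages by period ignore unequal time at risk, and the Observation Period split by Ig status has no valid denominator

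*SAP*

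**What the plan says.** SAP 10.2 sets the measure: "The number and percentage of participants who experience TEAEs will be summarized by Treatment Period, Observation Period" and Overall, by treatment group. On table content it says: "Summary tables will contain counts of participants, percentages of participants in parentheses and the number of events". SAP 10 sets the analysis set: "All safety analyses will be presented using the SS" (the Safety Set). No denominator specific to a period or to an Ig stratum is given for these tables.

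The windows are also in SAP 10.2. A TEAE belongs to the Treatment Period if it starts "at the time of or after the first administration of IMP on Day 1, up to Visit 17/PEOT (non-inclusively"). From Visit 17/PEOT until 8 weeks after the last IMP dose it belongs to the Observation Period. Observation Period TEAEs are then split by whether the participant received Ig "between start of the Observation Period and occurrence of the TEAE".

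Three rules decide how long a participant stays in each window:

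- Protocol 6.4 lists this among the events that require IMP to be discontinued: "Subject is treated with rescue medication and/or relapses during the Treatment Period". Protocol 8.4 then schedules a PEOT visit as close as possible to that decision.
- SAP 2.3 offers direct OLE entry only to those who complete treatment without relapse, and Visit 17 is then their last visit: "The Observation Period will be limited to 1 week for these subjects".
- Relapsed or withdrawn participants, and completers who decline the OLE, may return to Ig during the Observation Period and remain under follow-up.

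On exposure, SAP 10.1 covers only percentage deviation from the intended dose. Days on study medication appear only in the discontinuation listing of SAP 5.1.

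**The concern.** Safety and tolerability is a secondary objective, and these period tables are its main between-arm display. A percentage with a fixed denominator reflects both how often events occur and how long people were watched. Here the length of watching depends on efficacy, so an arm with fewer relapses is observed longer in the Treatment Period. It also has more people eligible to leave at Visit 17, and so less time in the Observation Period. Two arms with identical event hazards could then show different percentages, in opposite directions in the two columns.

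The Ig split is a separate fault. It classifies events, yet the table reports participants. A programmer would have to invent a denominator that the plan does not define.

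**Working it through.** **1. The plan's own figure.** SAP 2.4 gives 15 per group, one-sided 5%, 80% power at effect size 0.93 and 40% at 0.52. A noncentral t calculation (28 df, noncentrality d × √(15/2)) returns 0.7995 and 0.3993, and 30/(1 − 0.10) = 33.3, rounded up to 34. The figures reproduce and are not in dispute; they supply 17 per arm. The documents give no TEAE or relapse rate, so every rate below is an assumption.

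**2. Windows under SAP 10.2.**

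| Participant | Treatment Period | Observation Period |
|---|---|---|
| Completer who stays | Day 1 to Visit 17 (Day 85): 12 weeks | Day 85 to Day 78 + 56 = 134: 49/7 = 7 weeks |
| Completer, direct OLE entry | 12 weeks | about 0 weeks |
| Relapse with PEOT at week 5 | 5 weeks | to last dose + 8 weeks: about 7 weeks |

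The one week in SAP 2.3 lies before Visit 17, so SAP 10.2 counts it in the Treatment Period. SAP 3.2.2 and Protocol Table 5-1 start the Observation Period the day after the last dose or Visit 16. SAP 10.2 starts it at Visit 17/PEOT.

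**3. Treatment Period, equal hazards.** Incidence over w weeks is 1 − exp(−hw). With h = 0.05: 5 weeks 22.1%, 12 weeks 45.1%.

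- Placebo, 50% stopping at week 5: 0.5 × 22.1 + 0.5 × 45.1 = 33.6%; mean window 0.5 × 5 + 0.5 × 12 = 8.5 weeks.
- Active, 20% stopping: 0.2 × 22.1 + 0.8 × 45.1 = 40.5%; mean window 0.2 × 5 + 0.8 × 12 = 10.6 weeks.
- Difference: +6.9 points.

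In general the difference is (placebo stop share − active stop share) × (e^(−5h) − e^(−12h)). With active at 20%:

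- Smallest: h = 0.03, placebo 40%: 0.2 × (0.861 − 0.698) = 3.3 points.
- Largest: h = 0.08, placebo 60%: 0.4 × (0.670 − 0.383) = 11.5 points.
- Equal stopping: 0.
- Shares exchanged (placebo 20%, active 50%), h = 0.05: −6.9 points.

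A second model spreads stopping exponentially over the 12 weeks. With a 12-week TEAE risk of 50% and stopping of 50% against 20%, it gives 37.5% against 45.4% (+7.9). Over TEAE risks of 30–70% and stopping of 30/10, 50/20 and 70/30%, the range is +3.1 to +15.4, or +2.0 to +9.9 if 60% of the hazard falls in the first 3 weeks. With stopping of 20% on placebo and 50% on active, it is −5.0 to −10.2 with a constant hazard.

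**4. Observation Period.** Take a 12-week TEAE risk of 50% (weekly hazard ln 2/12 = 0.0578), so 7 weeks gives 1 − exp(−0.404) = 33.3%. With relapse of 50% against 20%, 80% of completers entering the OLE, and Safety Set denominators:

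- Placebo: 33.3 × (1 − 0.5 × 0.8) = 20.0%.
- Active: 33.3 × (1 − 0.8 × 0.8) = 12.0%.

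If nobody enters the OLE, both are 33.3%.

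**5. Overall.** In the simple model, a week-5 stopper last dosed on Day 29 is followed to Day 29 + 56 = 85, the same day as a direct OLE entrant. If every completer enters the OLE, the difference is 0. In the exponential model (TEAE risk 50%, relapse 50% against 20%) it runs from −0.2 with full OLE uptake to +4.8 with none. The largest value in any setting run was +7.2 (relapse 70% against 30%, no OLE entry).

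**6. Precision.** For 33.6% against 40.5% at 17 per arm: √((0.336 × 0.664 + 0.405 × 0.595)/17) = 0.165, or 16.5 points. Across the scenarios it is about 14 to 17 points.

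**7. What a rate does.** Expected time to first event or stop is incidence/h: 0.336/0.05 = 6.7 weeks on placebo and 0.405/0.05 = 8.1 on active. Events over person-time return 5 per 100 participant-weeks in both arms.

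**8. Ig strata.** The classifying interval ends at the TEAE. A participant without one has no end date and fits neither stratum. A participant with one TEAE before the first Ig dose and another after it falls in both. The strata therefore do not partition the participants, and dividing by the whole Safety Set would understate both.

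**The case against.** The strongest reply is that little harm follows. The safety summaries are descriptive, with no test or decision rule attached, and 6.9 points is less than half of one standard error at 17 per arm. Event counts accompany the percentages, the AE listing gives days since first and most recent dose, and Kaplan-Meier displays of relapse and rescue are planned. A careful reader could detect unequal follow-up. All of this stands, and it makes the matter one of interpretation.

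Some stronger readings are tempting but not supported:

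- That an effective drug will look less safe in general. This applies to the Treatment Period column, and only if active stops less often. Protocol 6.4 also foresees stopping for infusion reactions, severe headache and gastrointestinal events, which could reverse it. The Overall column largely rebalances.
- That the Observation Period contrast is 1 week against 8. That takes the period start from the design sections; under SAP 10.2 it is about 0 against 7. It also compares OLE entrants with stayers, not arm with arm.
- That Ig restart ends follow-up. It only moves later events to the other stratum.

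The reply does not reach the Ig strata, whose fault depends on no assumed rate and no sample size.

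**Conclusion.** The point holds in two parts of unequal strength.

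The firmer part is the Ig split: as written, its participant percentages have no valid denominator, whatever the event rates.

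The other part is conditional. If relapse differs between arms, the period percentages mix hazard with follow-up. The Treatment Period gap with equal hazards is +6.9 points under the stated assumptions (3.3 to 11.5 over 3–8% per week and 40–60% placebo stops, with active at 20% and all stops at week 5). It is zero with equal stopping and reverses if active stops more. It runs in the active arm's favour in the Observation Period when active relapses less and completers enter the OLE. Overall it is about −0.2 to +4.8 points in the central setting. No test is affected. The change should be made because the distortion is systematic and cheap to remove.

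**What to change.** In SAP 10.2, beside the existing counts and percentages, add by arm: person-time, exposure-adjusted first-event incidence (participants with a first event per 100 participant-weeks) and event rates. Give these for the Treatment Period, Observation off Ig, Observation on Ig, and Overall. Replace the on/off-Ig percentages by these rates.

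- **First-event incidence:** end person-time at the earliest of first event, end of that period, OLE entry, withdrawal or last contact, and last IMP plus 8 weeks.
- **Event rates:** use the same limits, but do not stop at the first event.
- **Ig as time-varying:** off-Ig time ends and on-Ig time starts at the first Ig dose. Ig restart does not censor Overall. State a same-day convention, because SAP 4.2.7 notes that medication times are not recorded.
- **Number at risk:** show how many enter the Observation Period in each arm.
- **Period start:** reconcile SAP 10.2 with SAP 3.2.2 and Protocol Table 5-1.

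The dose, visit, AE onset, medication and last-contact dates are already in planned listings, so the cost is some programming and wider tables. Rates assume a roughly constant hazard, which early clustering of events would break; a time-to-first-TEAE display is a useful companion.
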